Hypotheses: The primary hypothesis is that the program will be deemed an acceptable and feasible method of improving physical activity participation among individuals with SCI who ambulate. A secondary hypothesis is that the program will improve basic psychological needs and autonomous motivation to participate in LTPA. A tertiary hypothesis is that the program will increase leisure-time physical activity levels, quality of physical activity participation, and employment.

2. MEASURES (Appendix A)

The following section on Feasibility and Engagement will not require any additional effort or information from participants, but rather assesses the study progression to understand whether the intervention is feasible for future implementation.

Feasibility and Engagement

Feasibility will be assessed according to **process, resource, management, and scientific** indicators (Adamson et al., 2016; Learmonth & Motl, 2018).

Process feasibility assesses participant recruitment. A recruitment rate (dividing the total number of participants enrolled by the number of participants contacted) and eligibility rate (number of potential participants excluded from the total number of interested participants) will be calculated. We will aim to have a recruitment rate of 60% and eligibility rate of 55% as reported by Jeske and colleagues (2020) in a physical activity intervention for individuals living with SCI.

Resource feasibility assesses participation and monetary requirements of the study. Participation will be examined through retention rate (number of participants who completed at least some part of the intervention from those who were randomized) and adherence rate (number of participants who completed testing and follow-up measures). We will aim to have a retention rate of 90% (physical activity intervention for individuals with SCI; Jeske et al., 2020) to 100% (used at least one part of mobile health application; Smith et al., 2017) as reported by similar interventions. We will aim to have an adherence rate of 81-90% (Allin et al., 2020). We will assess the costs of the study as calculated by the total cost for producing the software and app, participant remuneration, and potential cost of the health behaviour coach.

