Management feasibility assesses data management and safety reporting during the study. We will record the IRB approval time according to the total number of days from submission to approval notification including any amendment details as necessary. Next, we will report staff preparation and reporting time calculated as the time to: recruit partners, conduct partner interviews, analyze recommendations, recruit participants, liaise with participants (e.g., group allocation, answering questions), and enter and check all participant data (i.e., total minutes). Missing data items (i.e., questions not answered for testing) will be monitored for baseline and follow-up assessments.

Scientific feasibility assesses the safety, burden, and treatment effect of the study. Safety will be recorded as the number of health problems experienced by the participants over the course of the intervention. Demographic information will be established via a self-report questionnaire. We will describe measures for assessing participant satisfaction and burden below in the qualitative measures section. Compliance with the intervention will be calculated according to the number of participants who complete each weekly module. Although participant compliance is high for traditional physical activity interventions for people with SCI (88% to 91.7%; Brawley et al., 2013; Jeske et al., 2020), we expect much lower compliance for an app-based intervention. Notably, one intervention states that compliance ranges from 16% to 100% depending on the module. As such, we expect to see different compliance rates throughout the course of the intervention. Finally, treatment effects will be assessed according to the quantitative measures listed below.

Engagement with the app will be measured in different ways. First, we will measure compliance as stated above. Next, we will assess the number of times logged into the app over the course of 8-weeks. Finally, we will look at how long each participant spends logged into the app during each module. Previous research suggests that web users spend significantly longer on

interventions compared to app users, but app users log into interventions significantly more times than web users (Morrison et al., 2018).

Outcome Measures

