3. RESEARCH DESIGN/PROTOCOL

This randomized controlled trial will examine the feasibility and acceptability of a mHealth application called Stronger Together. Stronger Together is an app that hosts programs for individuals with chronic illnesses and disabilities. In this study, we are developing and testing the Stronger Together program that aims to improve the quantity and quality of physical activity among ambulators with SCI. Furthermore, the study will also collect pilot data on the magnitude of the effects on physical activity participation (quality and quantity) and psychosocial influences on physical activity. Individuals living with SCI who walk and live in Canada, or the United States will be recruited for this study and will be assigned to either a wait-list control or intervention group. The wait-list control group will be instructed to maintain their current health habits and that we would prefer them to not to engage in any new physical activity programs for the next 8-weeks. This is to ensure that potential program effects are independent of any other physical activity program, which is a standard protocol among physical activity randomized controlled trials. The wait-list control group will be invited to access the intervention after 8-weeks.

Potential participants will be immediately directed to complete the consent forms/baseline measures in Qualtrics. Once consent and baseline measures are completed, participants will be randomized into either the wait-list control or intervention condition. We will aim to recruit at least 8-10 participants with consent and baseline measures completed before randomization into conditions in order for there to be enough participants in the program at the same time for peer support. After the first 8-10 participants, we will randomize individuals immediately after baseline testing so that individuals randomized to the intervention group can join others in the app right away. Randomization will be done by [name] [name] using a random numbers generator in blocks of 2 and 4 with even groups in each condition (i.e., n=10 per condition). Waitlist-control participants will be directed to continue their normal daily activity.

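### The retention rate is written over everyone randomised, half of whom are wait-list controls without the app until after week 8; the denominator should be the intervention arm, with a stated window

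*Combined protocol and SAP*

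**What the plan says.** Section 2 (Measures, Feasibility and Engagement) gives two participation rates under resource feasibility. The first is the "retention rate (number of participants who completed at least some part of the intervention from those who were randomized". For the aim it says "We will aim to have a retention rate of 90" per cent, rising to 100%. Both ends are taken from similar interventions, and the 100% benchmark is glossed as "used at least one part of mobile health application". The definition names no arm and no period over which use is counted.

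Section 3 (Research Design/Protocol) randomises "with even groups in each condition (i.e., n=10 per condition"), out of a planned total of 20. On the controls it says: "The wait-list control group will be invited to access the intervention after 8-weeks". Until then they are told to carry on as normal. The Summary schedules assessments for both groups at baseline, week 4 and week 8, and describes none after that.

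Section 3 also sends intervention participants to download the app, encourages the intervention group to use it at least weekly, and has the coach remind people who have not engaged. Section 8 (Data Analysis) does not mention retention.

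**The concern.** The numerator counts people who have done something in the app. The denominator, read as written, includes people who are not offered the app during the 8 weeks. A control who follows the protocol exactly therefore counts as not retained at week 8.

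The primary hypothesis is that the program is acceptable and feasible. Retention is one of four feasibility rates with a numeric aim; the others are recruitment, eligibility and adherence. If the base is settled only after the data are in, the same counts can be reported as an aim missed or an aim met.

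**Working it through.** **Inputs**
- Total randomised, N = 20 (Summary; section 4).
- Intervention arm 10, wait-list arm 10 (section 3). Check: 10 + 10 = 20, which agrees with the stated total.
- Aim 90% to 100% (section 2). It is a benchmark from other studies, so there is no calculation in the plan to reproduce.
- Controls able to use the app by week 8: 0 (section 3).

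**Formula.** Retention = participants who completed at least some part of the intervention / participants in the denominator.

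**1. Denominator as written, counted at week 8.** The largest possible numerator is 10 + 0 = 10, so the ceiling is 10/20 = 50%. If incomplete blocks left an 11:9 split, the ceiling would be 11/20 = 55% or 9/20 = 45%, still well below 90%.

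**2. Denominator as written, no end to the window.** The ceiling is 20/20 = 100%. The lower aim needs 0.90 × 20 = 18 users. If all 10 intervention participants use the app, 18 − 10 = 8 of the 10 controls must also do so. If 9 use it, 18 − 9 = 9 controls are needed.

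**3. Intervention arm as denominator.** The ceiling is 10/10 = 100%, and the lower aim needs 0.90 × 10 = 9 users.

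**Same data, two bases (intervention-arm users by week 8)**

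| Users | Of all 20 randomised | Of the 10 in the intervention arm |
|---|---|---|
| 8 | 40% | 80% |
| 9 | 45% | 90% |
| 10 | 50% | 100% |

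With 9 or 10 users the choice of base decides whether the aim is met. With 8 it is missed on either base.

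**Which base was meant.** The gloss on the 100% benchmark is about using the app. Section 3 ties downloading, weekly use and reminders to the intervention group. The log-in count in section 2 has an explicit period: "we will assess the number of times logged into the app over the course of 8-weeks". All of this points to the intervention arm over 8 weeks, but none of it is in the retention definition.

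**The case against.** The strongest reply is that no careful analyst would divide by 20. One can only complete part of an intervention one has been given, section 3 directs only the intervention group to the app, and the benchmark concerns app use. On that base the aim is attainable. This stands as evidence of intent, and it is why the point is minor. It does not remove the mismatch, because the definition does name a denominator and it is those randomised, in a trial that randomises both arms. The neighbouring adherence rate does not help: it counts completed assessments, which both arms undergo, so the two rates plausibly need different bases.

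A second reply is that the literal text sets no week-8 cut-off and controls are offered the app later, so the aim is not ruled out. That is correct. A reader might infer that the retention target is impossible or that the plan contains an arithmetic error. The documents support neither: the 50% ceiling holds only if the rate is computed at week 8, and no stated figure fails to reproduce.

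A third reply is that little turns on the figure. No progression rule, test or sample size depends on it, and in a 20-person trial the arm-level counts would let readers recompute it. This also stands and limits the weight of the point.

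A reader might extend the criticism to weekly-module compliance, where "Compliance with the intervention will be calculated according to the number of participants who complete each weekly module" and no denominator is given. That is missing detail and not a stated rule that misfires. No target is attached; the plan expects varying rates and notes another intervention in which "compliance ranges from 16% to 100% depending on the module". Stating that denominator is an optional clarification.

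**Conclusion.** The point holds as a minor correction to an outcome definition. As written, retention computed at the week-8 end of assessments is capped at 10/20 = 50% against an aim of 90% to 100%. With later use counted, 90% needs at least 8 of 10 controls to accept an optional offer. On the base almost certainly intended, 9 of 10 meets the aim, while the written denominator gives 45% for the same people.

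This rests on the planned 10:10 split and on the section 3 rule that controls wait. Section 4 (Recruitment) tells eligible participants how to download the app without naming an arm. Taken alone, that might suggest that controls get the app too, but section 3 is explicit that they wait. The missing arm and window are certain from the text; the 50% figure is conditional on the week-8 reading.

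**What to change.** In section 2, under resource feasibility, define retention as the number of participants who used at least one part of the app during the 8-week program, divided by the number randomised to the intervention arm (planned n=10). Keep the 90% to 100% aim. Report any app use by controls after week 8 separately, as description only.

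The cost is a change of wording. It needs no new data and leaves the design, sample size and assessments unchanged. Stating the weekly-module compliance denominator and giving an exact confidence interval for retention would be reasonable additions, but this correction does not depend on them.

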Intervention participants will be directed to the App store to download the Stronger Together app to proceed with app registration. Participants will then be connected with the community coach who is a ‘real live person’ who monitors in-app activity (this will be the program lead, SL). Other in-app features include peer discussion groups, behavioural support, and educational modules to support strategies to increase the quantity and quality of physical activity.

The 8-week program features weekly blocks of content. Each week builds from the previous week and targets specific components related to the three basic psychological needs (autonomy, relatedness, competence). The overall cadence of each weekly block is maintained throughout. For example, each week contains: 1) education modules 2) a worksheet or guided practice to apply the strategies in their own goals for that week along with embedded questions to discuss with their community coach 3) behavioural support from the community coach and 4) peer support from the discussion group. Participants in the intervention group will be encouraged to use the app as often as needed (but at least once per week) and actively participate in the programming. The community coach (SL) will prompt participants who have not engaged in the app in a week to remind them to complete weekly modules. In-app data, including user metrics will be collected and analyzed for descriptive patterns and assess correlations with the outcome measures (e.g., is the amount of time spent in-app correlated with changes in behaviour).

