Participants in both the intervention and control groups will be asked to participate in eight online questionnaires provided through the survey platform Qualtrics at three different time points (baseline/onboarding, 4- and 8-weeks of using the Stronger Together program). A link to these questionnaires which will be hosted on Qualtrics will be emailed to all participants. Participants in both groups will also complete a 5-minute demographic questionnaire at the beginning (baseline) of the study. Outcome measure included in the online surveys will include the following: basic psychological needs (The Psychological Need Satisfaction in Exercise Scale); autonomous and controlled motivation (The Treatment Self-Regulation for Exercise Scale); social support (Sallis et al., 1987); action control (Snihotta et al., 2005); behaviour change constructs (Determinants of Physical Activity Questionnaire); leisure-time physical activity (LTPAQ-SCI); quality participation (MeEAP); and employment (CHART-SF).

After completing the final online survey (at 8-weeks), participants in the intervention group will be invited to participate in an interview to further explore their experiences and to increase our understanding of factors that influence acceptability and satisfaction of the Stronger Together program. The interview will be structured whereby the participant will go through the application with the interviewer to discuss components that they liked and disliked. This will provide a greater understanding of user engagement. Interviews will take place through video conferencing software. The interviews will be audio recorded to transcribe and code for analyses. The interviewer will confirm their consent verbally at the start of the interview.

Additionally, feasibility metrics will be kept and recorded by the program lead (SL) throughout the duration of the study. These metrics are related to process, resource, management, and scientific feasibility. More information on the feasibility metrics can be found in the research proposal (Appendix A).

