6. ADVERSE EVENTS

We do not think there is anything in the study that could harm or be bad for the participants. However, the following may happen in the study: Questionnaires, interview and intervention

programming: Occasionally, answering questions about feelings and experiences may make participants feel uncomfortable. Participants are not required to answer all of the questions and may skip any that make them feel uncomfortable or bring up any of their concerns. Participants that do experience an emotional reaction (e.g., distress) during programming, surveys or interviews will receive a list of resources that they may access (e.g., for mental health concerns). There is also a live coach who monitors the app and can respond directly to participants who have concerns.

It is possible that the actions taken to achieve set goals (as encouraged by the weekly content) may lead to an adverse event (e.g., a fall during walking that results in a fracture, if increased walking was something that the participant wanted to do). During the consent process, participants will be advised that if such a situation occurs to receive medical attention and to report such instances to the project coordinator. Additionally, during the consent process, individuals will be advised that information provided by the health coach should not be prioritized over advice given by their health professionals, and that if they have such concerns that this should be raised with the health coach, and if not resolved then with the project coordinator.

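### No solicited health-problem question supports the safety count, so it is likely to be incomplete and, if controls are counted, may be ascertained unequally by arm

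*Combined protocol and SAP*

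**What the plan says.** **The measure.** Section 2 (Measures, Feasibility and Engagement) lists safety under scientific feasibility: "Safety will be recorded as the number of health problems experienced by the participants over the course of the intervention". It gives no definition of a health problem, no instrument, no schedule and no presentation by arm. The opening of the same section says that the feasibility and engagement measures "will not require any additional effort or information from participants".

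**The scheduled surveys.** Section 3 (Research Design/Protocol) states: "Participants in both the intervention and control groups will be asked to participate in eight online questionnaires", at baseline, 4 weeks and 8 weeks. The list that follows covers psychological needs, motivation, social support, action control, behaviour-change constructs, leisure-time activity, quality of participation and employment. No health-problem item appears.

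**The reporting route.** Section 6 (Adverse Events) foresees that pursuing activity goals could lead to harm, with a fracture after a fall as its example. During consent, "participants will be advised that if such a situation occurs to receive medical attention and to report such instances to the project coordinator".

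**Contact by arm.** Section 3 says of the intervention arm: "Participants will then be connected with the community coach who is a ‘real live person’ who monitors in-app activity". The coach also "will prompt participants who have not engaged in the app in a week to remind them to complete weekly modules", and section 6 adds: "There is also a live coach who monitors the app and can respond directly to participants who have concerns". Intervention participants are invited to an interview after week 8. Controls carry on as usual and are offered the app only after 8 weeks. The program lead acts as coach and also records the feasibility metrics.

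**The concern.** Feasibility is part of the primary hypothesis, and safety is one of its indicators. If nobody is asked about health problems, the count depends mainly on who comes forward. A low count could then be read as reassurance about a programme that encourages activity, when it partly reflects silence.

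A second issue depends on an ambiguity. The safety sentence does not say whether controls are counted. If they are not, the trial has no background rate against which to read the intervention count. If they are, the intervention arm has two extra channels through which a problem could come to light, the coach and the interview. Any excess in that arm could not then be separated from better ascertainment.

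**Working it through.** The plan gives no safety rate, capture rate or safety threshold, so there is no figure to reproduce. The main check is a reading of the text; the arithmetic only shows scale.

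**Step 1. Is a health-problem question described anywhere?**
- Section 2 says the feasibility measures, safety among them, ask nothing extra of participants.
- Section 3 lists the content of the surveys sent to both arms; none of the eight instruments is described as a safety measure. The CHART-SF, which might have touched on health, is cut to two items on working hours and earnings.
- Section 6 describes a route that the participant must start.
- Result: no solicited item is described in either arm.

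**Step 2. Does contact differ by arm during the 8 weeks?**

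| Channel | Intervention | Control |
|---|---|---|
| Consent advice to report to the coordinator | yes | yes |
| Surveys at weeks 4 and 8, no health-problem item described | yes | yes |
| Activity recall (LTPAQ-SCI), described in section 2 as administered by the student investigator | yes | yes |
| Coach monitoring, reminders and response to concerns | yes | no |
| Exit interview after week 8 | yes | no |

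**Step 3. Illustration of unequal capture.** From section 3, n = 10 per arm. Assumed, with no source in the documents: true 8-week risk p of at least one health problem, equal in both arms, and the probability c that an affected participant is recorded. Expected number of participants recorded = n × p × c.

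- p = 30%, c = 90% v 50%: 10 × 0.3 × 0.9 = 2.7 v 10 × 0.3 × 0.5 = 1.5. Treating the counts as independent binomials, the intervention count is higher with probability 0.65 and the control count with probability 0.17.
- p = 30%, c = 70% v 50%: 2.1 v 1.5 (0.52 v 0.26).
- p = 10%, c = 90% v 50%: 0.9 v 0.5. p = 50%: 4.5 v 2.5.
- p = 30%, c = 90% in both arms: 2.7 v 2.7, each arm higher with probability 0.40.

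The expected ratio is the ratio of the capture rates: 0.9/0.7 = 1.3 and 0.9/0.5 = 1.8.

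**Step 4. Illustration of incompleteness.** With 0 of 10 recorded, the exact two-sided 95% upper limit for the recorded risk is 1 − 0.025^(1/10) = 0.3085. The recorded risk is p × c, so the upper limit for p is 0.3085/c:
- full capture: 31%
- c = 90%: 0.3085/0.9 = 34%
- c = 70%: 0.3085/0.7 = 44%
- c = 50%: 0.3085/0.5 = 62%

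With p = 30% and c = 50%, an arm shows no reports at all with probability (1 − 0.15)^10 = 0.20.

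**The case against.** The strongest reply is that the plan leaves a gap and does not lay down a faulty rule. Section 2 names the count without saying how it is collected. Section 6 is participant-protection text and is not declared to be the sole source of the count. Section 3 has the program lead record feasibility metrics throughout, without naming sources. A reader might infer that problems are counted only when volunteered; the documents do not say so. This stands and limits the claim to the absence of any described solicitation.

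The plan also makes no safety comparison between arms: safety is not among the outcome measures in section 2, and section 8 (Data Analysis) names no safety analysis. A reader might infer a planned contrast that is biased. The text does not support that, so the point about arms has to be conditional.

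Contact is less lopsided than it may look. The coordinator route is open to everyone, and the coach's reminders concern modules and not health. However, the consent advice follows a sentence about harm from goals set through the weekly content, which controls do not receive during the 8 weeks, so they may see less reason to report.

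Finally, the text of Appendix A is not available here, so the survey content is known only from descriptions. Section 2's statement that nothing extra is asked makes an undescribed safety item unlikely, but does not exclude it.

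**Conclusion.** The point holds in a limited form. A feasibility indicator is to be counted without any described question that would elicit it, so the count is likely to be incomplete. This stands even if the arms are never compared. If controls are counted, ascertainment may also differ by arm. The probable direction is more complete capture in the intervention arm, but that is an expectation and the documents do not establish it.

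The size is unknown. The figures above rest on assumed risks and capture rates, and the 62% limit should not be attached to the intervention arm without care: it needs 50% capture, whereas at 90% capture the limit is 34%, little different from 31%. The claim that the two counts will differ for non-causal reasons goes further than the text allows.

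This is a cheap improvement to one descriptive indicator in a 20-person feasibility trial. It does not threaten the trial's other measures.

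**What to change.** 1. Add one identical item to the existing week-4 and week-8 surveys in both arms: any new or worsened health problem, injury or fall since the last survey (yes/no, with a short description and whether care was sought). Define a health problem accordingly.
2. Amend the statement at the start of Feasibility and Engagement in section 2 that nothing further is asked of participants, since the new item contradicts it.
3. State that both arms are counted over weeks 0–8.
4. Report, descriptively and by arm, the number and proportion of participants with at least one solicited problem. Show how many answered the item, because section 6 lets participants skip questions.
5. List spontaneous, coach-received and interview reports separately, so that channels open to one arm only do not enter the comparable count.

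The cost is one question at two existing surveys, one extra table and an edit to section 2. The survey becomes slightly longer, and reported event counts will be higher than under the present plan; the report should say that this reflects asking.
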